2. STUDY OBJECTIVES AND ENDPOINTS

2.1 Objectives

The objectives of this randomized, rater-blinded clinical trial are to 1) determine the effects of OSA on specific domains of cognitive function in patients with MS; and 2) assess the effects of OSA treatment with positive airway pressure (PAP) therapy on cognitive dysfunction in MS patients.

2.2 Endpoints

2.2.1 Primary Endpoint(s)

Effects of PSG-derived standard measures of sleep disordered breathing (including RDI, ODI, minimum O₂ saturation), on cognitive test scores.

Effects of PAP therapy on cognition, as measured by mean change from baseline in cognitive test scores in Group 1 (expedited PAP therapy) compared to Group 2 (delayed PAP therapy).

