Furthermore, preliminary findings from the investigators suggest that sleep disturbances, and OSA in particular, could contribute to domains of cognitive dysfunction that are key aspects of morbidity in MS. If a causal role does exist, identification and treatment of OSA could provide new opportunities to improve cognition in MS patients. **This study will for the first time prospectively evaluate the effects of OSA severity and its treatment on multiple key domains of cognitive function most affected in patients with MS, while controlling for other sleep- and MS-related variables that may influence these relationships.**

Hypotheses

Hypothesis 1: Sleep apnea severity, as reflected by standard PSG measures [respiratory disturbance index (RDI), oxygen desaturation index (ODI), and minimum oxygen saturation (Min O₂)], as well as innovative new quantitative approaches, will be associated with reduced MACFIMS scores.

Hypothesis 2: Group 1, in comparison to Group 2, will show greater improvement from baseline in MACFIMS scores, on repeat MACFIMS testing at month 3.

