2.2.2 Exploratory Endpoints

Effects of standard and novel PSG-derived measures of sleep disturbances (including TST, WASO, TAI, SE, RCREC, and sleep stage dynamics) on cognitive test scores.

Mean change from baseline in subjective sleepiness, as measured by the Epworth Sleepiness Scale, in group 1 vs group 2;

Mean change from baseline in daytime fatigue level, as measured by the Fatigue Severity Scale, in group 1 vs group 2;

Mean change from baseline in insomnia level, as measured by the Insomnia Severity Index, in group 1 vs group 2;

Mean change from baseline in quality of life and chronic daily symptoms (fatigue, anxiety, pain) as assessed by the Patient Reported Outcomes Measurement Information System (PROMIS, www.nihpromis.org/), in group 1 vs group 2.

[figure not shown]

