7. ASSESSMENTS

7.1 Primary Endpoint Assessments

Cognitive performance (primary outcome measure of interest) will be assessed with formal neuropsychological testing (see section 6.2). Sleep apnea severity (primary predictor of interest) will be assessed with overnight polysomnography (see section 6.3).

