9.0 DATA ANALYSIS/STATISTICAL METHODS

9.1 Sample Size Determination

Estimates (means and standard deviations) are derived from our recent data that evaluated SDMT scores among MS subjects referred for overnight PSG, and previously published interventional studies in that evaluated the effects of medical interventions on components of the MACFIMS in MS patients. We have chosen to focus on SDMT score as the primary outcome variable of interest, as the SDMT encompasses multiple domains of cognitive function, is frequently used in MS clinical studies as a reliable measure of cognitive impairment, and is sensitive to changes in intervention.

Based on a power analysis of two sample means (unequal sample sizes, with 2:1 randomization) with a 0.05 two-sided significance level, and an estimated S.D. of 9, a total sample size of 140 subjects will have an 86.3% power to detect a 5-point difference in SDMT score between groups, on month 3 testing, for hypothesis 2. Similarly, using individual MACFIMS components as outcome variables (in separate models), a multiple linear regression power analysis shows that a sample size of n=140 subjects will yield 88% power to detect an R-square difference of 0.05 for the test predictor of interest (% PAP use per month, as a continuous measure), assuming the R-squared explained by the adjustment variables is at least 0.3.

Although we predict a low dropout rate due to the short duration of the study, if we assume a dropout rate of 15% (10 dropouts per group), we will still have a power of 81.2% power to detect a 5-point difference in SDMT score between groups, on month 3 testing.

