9.2 Analysis of Primary Endpoint

Aim 1: Multivariate linear regression models will be used to analyze the effects of baseline PSG-derived standard measures of sleep disordered breathing (including RDI, ODI, minimum O2 saturation), on individual cognitive test scores (continuous outcome variables of interest, in separate models) for Aim 1, controlling for other sleep, serological, and clinical variables. Additional models that use computed respiratory cycle-related EEG changes (calculated as the maximum difference between the mean EEG powers associated with each of the 4 respiratory cycle segments as predictor variables) will be used to evaluate the effects of respiratory-related cortical microarousals on cognitive test scores, controlling for other clinical and sleep-related variables. Separate models that use computed temporal patterns of sleep stages as predictors of cognitive test scores will also be constructed.

Aim 2: Multivariate linear regression models will be used to test the effects of Group effect on 3-month (“post”) cognitive test scores, controlling for baseline (“pre”) test scores. We will also examine the association of PAP use as a continuous variable, based on mean nightly hours of use per month, on 3-month individual cognitive test scores, controlling for baseline scores. Separate models will be used for each cognitive test of interest. Predictor variables that are unbalanced between groups despite randomization will be used as covariates in the analyses.

To evaluate early effects of PAP therapy on cognitive scores, sleep stage dynamics will also be assessed during PAP titrations to determine whether changes in sleep stage stability predict improvements on cognitive test scores in separate models.

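### Section 9.1 names SDMT as the primary outcome and powers Hypothesis 2 on it, but Hypothesis 2 and Sections 2.2.1, 7.1 and 9.2 do not carry this through, so the false-positive risk for Aim 2 is uncontrolled

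*Combined protocol and SAP*

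**What the plan says.** Section 9.1 makes a choice: "We have chosen to focus on SDMT score as the primary outcome variable of interest". It gives reasons for that choice and then states 86.3% "power to detect a 5-point difference in SDMT score between groups, on month 3 testing, for hypothesis 2", using a two-sided 0.05 level, an SD of 9, 140 subjects and 2:1 allocation. A second power statement in the same section (88%) covers individual MACFIMS components in separate models. Its predictor is PAP use as a continuous measure, not randomized group.

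The places that define and analyse the Aim 2 outcome do not mention SDMT:

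- Section 1.2, Hypothesis 2: Group 1 "will show greater improvement from baseline in MACFIMS scores, on repeat MACFIMS testing at month 3".
- Section 2.2.1: the PAP effect is primary "as measured by mean change from baseline in cognitive test scores in Group 1 (expedited PAP therapy) compared to Group 2".
- Section 7.1: "Cognitive performance (primary outcome measure of interest) will be assessed with formal neuropsychological testing", with a pointer to the whole battery in Section 6.2.
- Section 9.2, headed as the primary analysis: "Separate models will be used for each cognitive test of interest". It does not list the tests or rank them.

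Section 2.2 has only primary and exploratory endpoints. The between-group items in Section 2.2.2 are sleepiness, fatigue, insomnia and quality of life with daily symptoms, for example "Mean change from baseline in subjective sleepiness, as measured by the Epworth Sleepiness Scale, in group 1 vs group 2". No between-group cognitive score is placed there. The opening summary (Assessments) and Section 3 also mention composite scores, which Section 9.2 neither defines nor models.

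**The concern.** A reader cannot tell from the plan what result would confirm Hypothesis 2. Section 9.1 points to SDMT. The hypothesis, the endpoint definition, the assessment section and the analysis section point to an unranked group of scores, and the other scores have no lower tier to belong to.

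Suppose SDMT shows no group difference and a verbal memory score reaches p<0.05. Section 9.1 would count the trial as negative on its primary outcome. Sections 2.2.1 and 9.2 would let the memory result be presented as a primary finding. This is the trial's only randomized comparison. Section 5.2 leaves the PI, the co-investigators and the statistician unblinded, so a choice of deciding test that is still open during the study could be influenced by the data.

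**Working it through.** **1. Reproduce the stated power.** Inputs from Section 9.1: difference 5, SD 9, two-sided 0.05, N=140 at 2:1. Sections 5.1 and 6.4 give the split as about 93 and 47.

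- Standard error = 9 × √(1/93 + 1/47) = 1.611.
- Noncentrality = 5 / 1.611 = 3.104, with 138 degrees of freedom and critical t = 1.977.
- Power = 86.9% by noncentral t, or 87.4% by the normal approximation. The plan states 86.3%.
- After dropout, 80/40 gives 81.2%, which equals the stated figure. Taking 10 per group literally (83/37) gives 79.6%.

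The plan's SDMT arithmetic is sound. It describes one SDMT test at two-sided 0.05.

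**2. Count the outcomes the general wording could cover.**

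- Section 6.2 says MACFIMS uses 7 standard measures.
- Section 6.2 then describes ten tests. The NAART is given at baseline only, which leaves 9 repeated: SDMT, PASAT, CVLT-II, BVMT-R, JLO, COWAT, NHPT, Trail Making and Go/No-go.
- Several of these yield more than one score (PASAT at two rates, CVLT-II total and delayed recall, Trails A and B). The number of separate scores is therefore larger, but the plan does not fix it.

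**3. Illustrate the false-positive risk.** Assume no true group effect on any test, each test at two-sided 0.05, and any single significant result taken as support for Hypothesis 2.

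- Independent tests: risk = 1 − 0.95^k. For k=7, 1 − 0.698 = 30.2%. For k=9, 1 − 0.630 = 37.0%.
- Equally correlated normal test statistics with correlation r: risk = 1 − ∫ φ(s) [Φ((1.96 − √r·s)/√(1−r)) − Φ((−1.96 − √r·s)/√(1−r))]^k ds, integrated numerically.

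| Assumed correlation | 7 measures | 9 repeated tests |
|---|---|---|
| 0.7 | 17.8% | 20.2% |
| 0.5 | 23.0% | 26.9% |
| 0 | 30.2% | 37.0% |

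The documents give no correlations, so the rows are a range of assumptions. Splitting tests into separate scores raises every figure.

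**4. Effect on SDMT power.** Testing other scores unadjusted at 0.05 does not alter the SDMT test, so its power remains as in step 1.

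**The case against.** The best defence is that Section 9.1 already settles the matter. It names SDMT with a rationale, an effect size, a significance level and a matching power. On this view cognition is the primary domain, SDMT is the primary variable within it, and the general wording elsewhere is shorthand. That reading is available, and it means the fault may be no more than a designation written in one place only. It does not remove the fault. The designation sits in the sample-size section, while the sections that define and analyse the primary endpoint are silent on it and give the other scores no other status.

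Four stronger readings are tempting, and the documents do not support them:

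- A reader might infer that Section 9.2 sets up many co-equal primary tests at 0.05. It states no significance level, no equal ranking and no list of tests.
- A reader might infer that the stated power fails unless SDMT alone decides. It does not fail; only the overall false-positive risk changes. Power would fall if the significance level were divided among the tests, and no section proposes that.
- A reader might infer that Section 9.1 considers SDMT only. It also powers component-wise models, but against PAP use, which is not the randomized comparison.
- A reader might count every possible score and quote a much larger risk. Such a count depends on unstated choices, such as whether BVMT-R recognition is scored separately.

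The baseline-change wording in Section 2.2.1 is not a further conflict with Section 9.2. Once baseline is a covariate, the group coefficient is the same whether the outcome is change or the Month 3 score. The covariate rule in Section 9.2 ("Predictor variables that are unbalanced between groups despite randomization will be used as covariates in the analyses") is a separate matter and is not needed for this point.

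**Conclusion.** The concern holds as an inconsistency in the definition of the Aim 2 primary outcome. That all repeated cognitive scores are primary is an inference, though the natural one. The consequence is an uncontrolled false-positive risk for Hypothesis 2 in place of the nominal 5%: about 18% to 30% for 7 measures and 20% to 37% for 9 tests. Those figures rest on the assumed correlations and on an any-score rule that the plan leaves open. If SDMT alone decides, the risk is 5% and the stated power stands. The sample size calculation is not at fault. Because the ambiguity concerns which result decides the randomized comparison, it should be resolved before outcome data are examined.

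**What to change.** Carry the plan's own choice through.

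- In Hypothesis 2 (Section 1.2), Sections 2.2.1, 7.1 and 9.2, and the matching wording in the opening summary (Assessments and Statistical Methods), state that Hypothesis 2 is decided by the Group 1 versus Group 2 difference in Month 3 SDMT, adjusted for baseline SDMT, at two-sided 0.05.
- Label all other repeated cognitive scores secondary for Aim 2. Either name a multiplicity method for them or say they are reported unadjusted and are not confirmatory.
- Give any composite in the opening summary and Section 3 the same secondary status.
- Label the PAP-use models, including the one powered in Section 9.1, as supportive non-randomized analyses.

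The cost is wording only. N=140 and the stated SDMT power do not change. The sponsor gives up the option of claiming a positive result on another cognitive score as the primary result.

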2.2.2 Exploratory Endpoints

Effects of standard and novel PSG-derived measures of sleep disturbances (including TST, WASO, TAI, SE, RCREC, and sleep stage dynamics) on cognitive test scores.

Mean change from baseline in subjective sleepiness, as measured by the Epworth Sleepiness Scale, in group 1 vs group 2;

Mean change from baseline in daytime fatigue level, as measured by the Fatigue Severity Scale, in group 1 vs group 2;

Mean change from baseline in insomnia level, as measured by the Insomnia Severity Index, in group 1 vs group 2;

Mean change from baseline in quality of life and chronic daily symptoms (fatigue, anxiety, pain) as assessed by the Patient Reported Outcomes Measurement Information System (PROMIS, www.nihpromis.org/), in group 1 vs group 2.

[figure not shown]
3. STUDY DESIGN

N~175 patients who screen positive for high OSA risk on a validated screening questionnaire (STOP-Bang) given during routine MS Clinic appointments at the University of Michigan will be invited to participate. Additional subjects may be recruited from the community through a U-M electronic clinical trials registry (UMclinicalstudies.org); a clinicaltrials.gov posting; print or electronic newspaper advertisement; fliers at the medical center and in the community; and from study advertisements posted by the University of Michigan on Facebook and Twitter. Potential subjects who contact the study staff directly, or are referred by outside providers, and have not completed a STOP-Bang questionnaire, will be asked the STOP-Bang questions via telephone during a pre-screening interview. If their STOP-Bang assessment indicates a risk for sleep apnea (score ≥ 2 risk factors for sleep apnea), they will be invited to participate. If their STOP-Bang score is below a 2, they will not be eligible for the study.

Subjects who endorse a pre-existing diagnosis of OSA who are not yet using PAP therapy on a compliant basis - but who express an interest to start using it - will also be invited to participate.

Consenting subjects with elevated STOP-Bang scores or those who are at high risk for OSA will undergo baseline (month 0) PSG and baseline neuropsychological testing (MACFIMS) (see figure). Subjects who already have recent U-M in-lab PSG (within 1 year) indicating OSA will also undergo baseline cognitive testing, and their in-lab clinical PSG data will be used for baseline analyses. Subjects who have a diagnosis of OSA based on non-UM lab PSG or PSG > 1 year prior to screening will undergo baseline PSG and baseline cognitive testing.

Subjects who meet criteria for OSA on baseline or clinical in-lab PSG (n~140, anticipated) will then be randomized into one of two groups (2:1 randomization): immediate treatment with PAP (Group 1, n~93) followed by repeat neuropsychological testing at 3 months post-PAP; or standard of care application of PAP at 3 months post-randomization, after completion of repeat neuropsychological testing (Group 2, n~47). Analyses will focus on relationships between standard PSG measures (Respiratory Disturbance Index, oxygen desaturation index, and minimum oxygen saturation), innovative new quantitative PSG measures and MACFIMS scores, as well as mean changes from baseline in individual and composite MACFIMS scores following treatment with PAP therapy.

4. SUBJECT SELECTION

4.0 Subject Recruitment

The projected number of subjects for enrollment is N~175, all diagnosed with clinically definite MS. Subjects will be recruited from the University of Michigan (U-M) MS Clinic during routine appointments. An additional recruitment site will include a new, first-of-its-kind Sleep and MS Multidisciplinary Clinic, founded by the investigators (Drs. [name] and [name]). Additional subjects may be recruited from the community through a U-M electronic clinical trials registry (UMclinicalstudies.org); a clinicaltrials.gov posting; print or electronic newspaper advertisement; fliers at the medical center and in the community; and from study advertisements posted by the University of Michigan on Facebook and Twitter. Information on the study will also be available via letter to medical colleagues in the community, advertised on a posted flyer, advertised via the internet through the UM research recruiting website (<https://umclinicalstudies.org>), advertised on a registry of clinical trials run by the United States National Library of Medicine (NLM) at the National Institutes of Health (clinicaltrials.gov), and advertised on Craigslist.

4.1 Inclusion Criteria

- 1) Age of 18-70 years at screening
- 2) Diagnosis of clinically definite MS
- 3) Willingness to undergo in-lab baseline polysomnography (PSG) and positive airway pressure (PAP) titration (if needed)
- 4) Willingness to undergo 2 separate 90-minute cognitive testing sessions
- 5) Either one of the following:

Score of ≥ 2 sleep apnea risk factors on the "STOP-Bang" sleep apnea screening questionnaire. The STOP-Bang questionnaire is a screening tool consisting of eight items which reflect OSA risk factors. STOP-Bang scores of ≥ 3 indicate elevated risk for moderate-severe OSA in the general population, and scores as low as 2 are frequently seen in MS patients with OSA, based on previous data from the PI).

OR

Have a pre-existing diagnosis of OSA based on a previous overnight sleep study (either home study or in-lab) but have not yet started using PAP therapy on a compliant basis. *If OSA was NOT diagnosed by a U-M in-lab sleep study within the past year prior to screening, subjects must be willing to get new baseline in-lab U-M PSG as part of study.

- 6) Willingness to start treatment with PAP if OSA present

4.2 Exclusion Criteria

- 1) Physical, psychiatric or cognitive impairment that prevents informed consent, PSG, PAP use, or reliable longitudinal follow-up
- 2) Cardiopulmonary conditions that may increase sleep apnea risk
- 3) Current treatment, such as PAP, for obstructive or central sleep apnea
- 4) History of surgical treatment for OSA
- 5) Nervous system diseases other than MS that may predispose subjects to OSA (such as Parkinson's disease, amyotrophic lateral sclerosis, or recent stroke)
- 6) History of concomitant central nervous system disease that could influence cognition, such as large vessel territory stroke, Alzheimer's disease, Parkinson's disease, or Lewy body dementia
- 7) Concomitant systemic autoimmune disease with secondary central nervous system involvement (including CNS lupus or neurosarcoidosis).
- 8) Pregnancy
- 9) Evidence of clinical MS relapse within the last 30 days prior to enrollment
- 10) Systemic high dose steroid use (1 gram IV methylprednisolone daily for 3-5 days or equivalent) for an MS relapse within the last 30 days prior to enrollment
- 11) Unwillingness to initiate PAP therapy if clinically indicated
- 12) Severe depression at screening per the Patient Health Questionnaire-8 (PHQ-8)
(The PHQ-8 is a brief, self-administered questionnaire that evaluates core symptoms associated with major depressive disorder. Scores range from 0 to 24 based on the frequency and severity of depressive symptoms over the previous two weeks.)
- 13) Anticipated initiation, dosage change, or discontinuation in medications that could, per the opinion of the investigators, influence cognitive test scores from baseline to follow-up, including MS disease modifying therapies, hypnotic agents, narcotic-based medications, benzodiazepines, antispasmodics, or 4-aminopyridine
- 14) ESS scores ≥ 16 on baseline visit
- 15) Subjects with extreme OSA accompanied by signs of cardiopulmonary compromise (RDI > 60 respiratory events per hour with severe nocturnal hypoxia or unstable ECG rhythms on PSG), will be excluded unless they are randomized to immediate PAP arm
- 16) Any other condition or treatment that in the opinion of the investigator could affect subject safety or study eligibility

Table 1: STOP-Bang questionnaire	
Snoring	Do you snore loudly (louder than talking or loud enough to be heard through closed doors)?
Tired	Do you often feel tired, fatigued, or sleepy during the daytime?
Observed Apneas	Has anyone ever observed you stop breathing during your sleep?
Blood Pressure	Do you have or are you being treated for high blood pressure?
BMI	BMI more than 35 kg/m ² ?
Age	Age over 50 years old?
Neck circumference	Are you a male with a neck circumference greater than 17 inches, or a female with a neck circumference greater than 16 inches?
Gender	Are you a male?

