PAP Therapy: There may be skin irritation related to the **PAP** mask, and masks can be uncomfortable and create a feeling of claustrophobia. There are multiple choices and sizes for sleep masks, and the provider will work with the subjects to find the most comfortable mask. There may be difficulty tolerating the forced air, but the pressure settings can be adjusted by working with the sleep machine provider. Subjects might experience a dry stuffy nose which can be treated with a saline nasal spray or humidified air that can be run through the PAP machine. The providers of these machines are very familiar with resolutions to and they will try and assist subjects in order to resolve any issues.

Confidentiality: The records of this study will remain confidential and protected; however, there is a risk for a breach of confidentiality. This risk is minimal, because a number of precautions have been taken in order to protect confidentiality. All data collected will be kept secure and in a locked office. Records will be coded and identifying information (such as name and registration numbers) will be removed and stored on a key in a separate location so that confidential information cannot be traced back to the subject. Only authorized members of the research team will have access to study records.

Standard care PAP treatment arm (for Group 2): Given that most consequences of OSA take months to years to manifest (cardiovascular disease, metabolic syndrome), we do not anticipate any significant long-term side effects from deferring PAP for 3 months for Group 2. Identification of sleep disordered breathing will be facilitated by enrollment into this study. Nonetheless, to avoid hazardous short-term consequences of OSA caused by excessive

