sleepiness (e.g., motor vehicle accidents), ESS scores ≥ 16 on baseline or follow-up visits will be cause for study exclusion/discontinuation. This cutoff was chosen based on data that demonstrate an ordinal increase in risk of sleepy driving accidents with increases in ESS score, particularly in subjects with ESS scores > 15 . We will also consider extreme OSA (RDI >60 respiratory events per hour, or unstable ECG rhythms on PSG) to be exclusionary, regardless of ESS score. For subjects who are not considered to be high risk per these criteria, we do not expect the risk of participating in this trial and having no CPAP for 3 months to exceed the risk encountered in routine clinical practice, as wait times for sleep clinic evaluations, subsequent sleep clinic referral, PSG, CPAP titration, and CPAP initiation at home currently often amount to 3 months or longer at U-M sleep clinics.

Alternative treatments and procedures: This study does not include an intervention. Therefore, there are no applicable alternative treatments or procedures.

As with any research study, there may be additional risks that are unforeseeable.

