5. STUDY TREATMENTS

5.1 Allocation to Treatment (see also 6.4)

Randomization Process: Subjects who meet all Inclusion/Exclusion criteria, including OSA on baseline or clinical PSG, will be randomized (2:1 randomization) to expedited PAP therapy (Group 1, n~93), or standard care PAP therapy (Group 2, n~47), after the subject has signed consent, completed the baseline activities, Randomization will be stratified by sleep apnea severity (RDI < or >=30) to minimize imbalances in apnea severity between groups.

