6.4 Randomization

Randomization Process/Blinding: Subjects who meet criteria for OSA on baseline or clinical PSG (n~140, anticipated) will be randomized (2:1 randomization) to determine whether they will receive expedited PAP therapy (Group 1, n~93), or standard of care PAP therapy (Group 2, n~47). Computer-based randomization will be stratified by sleep apnea severity (RDI $<$ or ≥ 30) to minimize imbalances in apnea severity between groups. PSG technicians, PSG interpreters, and study staff who conduct and score neuropsychological tests will remain blinded to group allocation for the duration of the study. The subject, PI, co-investigators, coordinators, and statistician will not be blinded. **Subjects will be contacted with the randomization**

assignment that determines whether they will be scheduled for immediate PAP titration (Group 1) or delayed PAP titration after their month 3 cognitive testing.

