13. STUDY DISCONTINUATION CRITERIA

Stopping Rules for Safety Reasons

Subjects who demonstrate evidence of severe excessive daytime sleepiness (as evidenced by ESS scores ≥ 16 at baseline) will result in exclusion from study. Subjects with extreme OSA that is accompanied by signs of cardiopulmonary compromise or severe nocturnal hypoxia on baseline PSG will also result in study exclusion unless they are randomized to expedited PAP arm. In such cases, subjects will be referred for expedited sleep clinic follow-up.

Discontinuation of a Subject

In the event a patient drops out of the study or is discontinued due to protocol violations, all attempts will be made to exit the patient in accordance with the protocol requirements.

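### Extreme-OSA patients with cardiopulmonary compromise are removed from the delayed-PAP arm but kept in the immediate-PAP arm, so eligibility for the Aim 2 comparison depends on allocation

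*Combined protocol and SAP*

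**What the plan says.** Item 15 of Section 4.2 concerns extreme OSA with signs of cardiopulmonary compromise, defined as "RDI > 60 respiratory events per hour with severe nocturnal hypoxia or unstable ECG rhythms on PSG". Such subjects "will be excluded unless they are randomized to immediate PAP arm". Section 13 has the same exception: these findings "will also result in study exclusion unless they are randomized to expedited PAP arm".

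Section 5.1 sets a different order: "Subjects who meet all Inclusion/Exclusion criteria, including OSA on baseline or clinical PSG, will be randomized (2:1 randomization"). Section 6.4 likewise places the PSG before allocation: "Subjects who meet criteria for OSA on baseline or clinical PSG (n~140, anticipated) will be randomized (2:1 randomization"). Allocation is stratified by RDI below 30 versus 30 or more.

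Section 1.3 also covers extreme OSA, in a paragraph headed "Standard care PAP treatment arm (for Group 2"). There the condition is RDI above 60 "or unstable ECG rhythms on PSG) to be exclusionary, regardless of ESS score".

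For the Aim 2 analysis, Section 9.2 regresses the Month 3 score on group and baseline score, and adds: "Predictor variables that are unbalanced between groups despite randomization will be used as covariates in the analyses". The documents define no analysis set and do not say how Group 2 subjects removed under item 15 are to be handled.

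**The concern.** An exclusion that operates after allocation, in one arm only, makes the groups differ by design. Group 1 can contain patients with extreme, compromised OSA and Group 2 cannot. The Aim 2 contrast then mixes the effect of PAP with the effect of having this subgroup in one arm.

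The direction cannot be predicted. If these patients score lower at Month 3 than others with the same baseline score, the rule biases against PAP. If they respond more strongly to PAP, it biases in favour.

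The rule also leaves room for judgement. Severe nocturnal hypoxia has no numeric limit, and the decision matters only in Group 2. Under Section 5.2 the PI, co-investigators, coordinators and statistician all know the allocation.

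**Working it through.** **Order of events.** The PSG that defines the criterion precedes randomisation, and its RDI is the stratification factor. The criterion could therefore be judged before allocation. As item 15 is written, it cannot be judged until the arm is known, so the sequence in Section 5.1 cannot be followed for it.

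**Do the existing safeguards help?** Stratification at RDI 30 acts at allocation, and the removal comes afterwards. The covariate rule in Section 9.2 could bring RDI into the model. That helps in part, because Group 2 may still hold subjects with RDI above 60 but no compromise. The compromised subgroup itself has no Group 2 comparators.

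**The three wordings.** Item 15 needs RDI above 60 together with hypoxia or unstable ECG. Section 1.3 needs RDI above 60 or unstable ECG. Section 13 speaks of extreme OSA without a number. Section 1.3 has no arm exception, but it sits in a Group 2 paragraph, so that is an ambiguity and not a contradiction.

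**Reproducing the plan's power.** Section 9.1 gives SD 9, a difference of 5 SDMT points, two-sided 0.05 and N = 140 at 2:1. A two-sample t test with 93 and 47 gives 86.9%, against the stated 86.3%. With 80 and 40 it gives 81.2%, which matches the stated figure after dropout.

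**Size of the bias.** Let e be the share of randomised subjects who meet the criterion, and let the gap be their difference from others in baseline-adjusted Month 3 SDMT. Both are assumptions.

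- Kept in Group 1 = 93e; lost from Group 2 = 47e.
- Group 1 contains a fraction e of such subjects and Group 2 none, so bias = e × gap. For example, 0.05 × 5 = 0.25.
- SE = 9 × √(1/93 + 1/n2), where n2 is Group 2 after removal.
- Type I error comes from a noncentral t with noncentrality bias/SE.

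| e | Kept in G1 / lost from G2 | n2 | SE | Bias, gap 2 | Bias, gap 5 | Type I error, gap 2 | Type I error, gap 5 |
|---|---|---|---|---|---|---|---|
| 1% | 0.9 / 0.5 | 47 | 1.61 | 0.02 | 0.05 | 5.0% | 5.0% |
| 2% | 1.9 / 0.9 | 46 | 1.62 | 0.04 | 0.10 | 5.0% | 5.0% |
| 5% | 4.7 / 2.4 | 45 | 1.63 | 0.10 | 0.25 | 5.0% | 5.3% |
| 10% | 9.3 / 4.7 | 42 | 1.67 | 0.20 | 0.50 | 5.2% | 6.0% |
| 15% | 14.0 / 7.1 | 40 | 1.70 | 0.30 | 0.75 | 5.4% | 7.2% |

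The 15% row is an upper bound. If 40% of subjects had RDI of 30 or more (also an assumption), it would need 0.15/0.40 = 37.5% of that stratum to meet this narrow criterion.

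The SE uses the unadjusted SD of 9 from Section 9.1. The planned model adjusts for baseline score, so its SE would be smaller and the type I error somewhat higher for the same gap. The table gives orders of magnitude, not the error rate of the planned analysis.

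**The case against.** The rule has a sound safety motive: these patients should not have PAP deferred for 3 months. That stands, but it argues only against assigning them to Group 2. Excluding them before randomisation protects them equally.

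The stronger objection is size. The share is unknown and probably small. Item 15 is narrow, and other criteria in Section 4.2 apply whatever the arm: item 2 (cardiopulmonary conditions that raise apnea risk), item 14 (ESS of 16 or more) and item 16 (investigator judgement on safety). A 5-point gap remaining after baseline adjustment would equal the whole target effect. At a 2-point gap, type I error does not exceed 5.4% even at a 15% share. All of this stands and points to the low end of the table, though the documents cannot confirm it.

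The wording differences can also be overstated. Section 13 uses the term extreme OSA, which Sections 1.3 and 4.2 both tie to RDI above 60. The difference that matters is Section 1.3's either/or against item 15's requirement for both.

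None of this removes the arm condition, which both operative sections state outright.

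**Conclusion.** The concern holds. Item 15 and Section 13 make eligibility for the randomised Aim 2 comparison depend on the assigned arm, contrary to Section 5.1, and nothing in the analysis plan supplies the missing comparators. This conclusion rests on the text alone.

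The numerical effect rests on assumed shares and gaps. It is negligible at shares of 1% to 2% and modest at 10% or more, and its sign is unknown. The point should be fixed because the defect is certain, lies in a primary comparison and can be avoided cheaply, not because a large bias is likely.

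**What to change.** **Change.** Delete the arm exception from item 15 and Section 13. Give Sections 1.3, 4.2 and 13 one definition, with a numeric limit for severe nocturnal hypoxia taken from measures already listed in Section 6.3, such as minimum saturation or the share of sleep time at or below 88%. Apply it to everyone from the baseline or clinical PSG before randomisation. Subjects who meet it are not randomised, receive the expedited sleep-clinic referral that Section 13 already provides, and can still contribute to Aim 1.

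**Subjects already randomised.** Fix the cut-off blind to allocation and outcome. Have the blinded PSG interpreter classify every baseline PSG, and leave subjects who meet the criterion out of both arms in the primary Aim 2 analysis. Analysing everyone as allocated would be an alternative only if Month 3 scores exist for the Group 2 subjects who were removed.

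**Cost.** Future subjects need a wording amendment and no new procedure. Those already randomised need a one-off re-reading of existing PSGs. Power before dropout and without replacement, for 5 points and SD 9:

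| e | Current rule | After the fix (n1/n2) | Extra OSA-positive subjects to keep 140: 140/(1−e) − 140 |
|---|---|---|---|
| 1% | 86.9% | 86.8% (92/47) | 1.4 |
| 2% | 86.4% | 86.2% (91/46) | 2.9 |
| 5% | 85.9% | 85.3% (88/45) | 7.4 |
| 10% | 84.3% | 83.1% (84/42) | 15.6 |
| 15% | 83.1% | 81.0% (79/40) | 24.7 |

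The loss against the current rule is about 0.1 to 2 percentage points. With full replacement at the planned yield of 140 randomised from 175 enrolled, 1.4 to 24.7 extra subjects mean about 2 to 31 more enrolled (multiply by 175/140 = 1.25).
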